4.6 Bias Control Measures

Multicenter Study: A multicenter design ensures that the case sample is more representative compared to a single-center study, thereby reducing the potential for bias caused by systemic errors

unique to a single center. This enhances the generalizability of the study results.

Standardized Data Collection: The eligible patients meeting the inclusion within the specified time frame, will be enrolled in this study to avoid selection bias. This ensures the integrity of the population under study and minimizes the risk of bias introduced by arbitrary patient selection.

Training of Data Recorders: Data collection personnel will undergo comprehensive training to ensure that all data are captured uniformly, in accordance with predefined data collection protocols and eCRF standards. Regular data audits and quality control procedures will be implemented to ensure the accuracy, reliability, and completeness of the data.

Data Review: Prior to database lock, a data review meeting will be initiated by the data management team. Attendees will include the principal investigator, the sponsor, data managers, clinical monitors, and biostatisticians. The primary objectives will be to finalize the statistical analysis dataset, evaluate any unreported AEs, verify any outstanding data queries, and decide on database lock and the formal approval of population stratification decisions.

Investigator Training: All investigators involved in this clinical study are highly experienced in the relevant therapeutic area. Prior to study initiation, Clinical Research Associates (CRAs) will conduct thorough protocol training sessions to ensure investigators are fully knowledgeable about the study design, endpoint definitions, and operational procedures. Investigators will rigorously adhere to the inclusion criteria and will document clinical data according to protocol-defined procedures.

Clinical Study Monitoring: Regular on-site monitoring visits will be conducted to ensure strict adherence to the study protocol. Source Data Verification (SDV) will be performed on eCRF to verify that the data recorded are consistent with the original source documents.

Identification of Confounding Variables: Potential confounders will be systematically identified. Any variable suspected to be a confounding factor, based on existing evidence, will be carefully documented. Factors that may influence both the intervention and the outcome will be thoroughly considered, and data collection will be as comprehensive as possible to ensure robust adjustment for confounding in the final analysis.

Clinical Events Committee: Medical data requested in the protocol will be provided to Clinical Events Committee under patient information protection for review. The personnel requirements of the CEC member and the contact details of the corresponding personnel will be recorded in a separate file. Evaluation and adjudication of safety endpoints as specified in the protocol will be completed by an independent Clinical Event Committee, and the relevant provisions for evaluation are referred to in the Clinical Event Committee bylaws.

5 Statistical Considerations

5.1 Sample Size Estimation

Not applicable.

This study is an observational study that does not involve statistical hypotheses. Therefore, the plan is to collect data on as many patients as possible who received FRED treatment for intracranial aneurysms in China from May 2023 to May 2027, and as such, there is no specific sample size

estimation.

5.2 Statistical Analysis Datasets

The dataset will consist of all study patients who meet the inclusion and exclusion criteria.

5.3 Statistical Analysis Methods

5.3.1 Statistical Analysis Plan

Detailed information on statistical analyses will be described in a separate Statistical Analysis Plan (SAP), with the final version of the SAP to be completed prior to database lock. Statistical analyses will be conducted according to the predefined SAP. Any changes to the statistical methods outlined in this protocol before database lock will be documented in SAP. Any modifications to the finalized SAP after database lock will be documented in the Statistical Analysis Report (SAR) and Clinical Study Report (CSR).

5.3.2 General Principle of Statistical Analysis

This study is observational in design and does not involve statistical inference or hypothesis testing. The statistical analysis will be performed for this study using SAS® (version 9.4 or higher).

Descriptive statistics for continuous variables will include the number of observations, mean, standard deviation, median, minimum, maximum values, and quartiles (Q1, Q3). Categorical variables will be described using frequencies and percentages. Unless otherwise specified, the significance level will be set at 5%, and the Confidence Interval (CI) will be set at 95%.

5.3.3 Baseline Analysis

The demographic, clinical characteristics, and treatment information of the patients were statistically described. The methodology will adhere to standard principles.

5.3.4 Endpoint analyses

Descriptive analyses will be conducted on safety and efficacy endpoints. For binary endpoints, counts and percentages will be provided, with 95% confidence intervals (CIs) estimated using the exact binomial method. Survival endpoints will be assessed using the Kaplan-Meier method to estimate survival probabilities and calculate the corresponding 95% CIs, accounting for censored data. Continuous endpoints will be summarized with counts, means, medians, standard deviations, minimums, maximums, and interquartile ranges, along with their 95% CIs.

5.4 Stage Analysis

According to the requirements of NMPA, the collected data will be divided according to the following schedule, and the statistics and analysis of clinical data during the corresponding collection period will be completed once a year:

- During May 2023 to May 2025
- During June 2025 to May 2026
- During June 2026 to May 2027

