4.1 Overall Design and Selection Rationale

This is a post-market, retrospective, multi-center, observational clinical study.

The study plans to enroll patients who meet the eligibility criteria and have received at least one implantation of the observational device between May 2023 and May 2027. The retrospective data will be collected on baseline characteristics, information of procedure, and safety and efficacy endpoint to assess the safety and efficacy of FRED in the Chinese population. The efficacy endpoints include technical success rates and re-sheathing performance, the complete occlusion rate, and modified Rankin Scale (mRS) change from baseline. The safety endpoints include the rates of stroke, mortality, lesion-related symptoms or signs rate, lesion-related complication rate, adverse event, serious adverse event.

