** Each patient may have multiple follow-up information, all of which should be recorded and collected. The collected follow-up data will be divided according to the following follow-up points: 30 days after surgery, 3 months after surgery, 6 months after surgery, and 1 year after surgery, according to the principle of closest approach.

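### The annual stage analyses divide the data into separate calendar periods, so a patient's implant and later follow-up can fall in different analyses and the stage rates rest on truncated or mismatched follow-up

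*Protocol*

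**What the plan says.** Protocol Section 5.4, repeated in the synopsis, refers to the regulator's requirements and states that "the collected data will be divided according to the following schedule", and that "the statistics and analysis of clinical data during the corresponding collection period will be completed once a year". The periods are "During May 2023 to May 2025", "During June 2025 to May 2026" and "During June 2026 to May 2027". They are consecutive, and none restarts at May 2023.

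Four other places bear on this:

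- Section 4.1 enrols patients who "have received at least one implantation of the observational device between May 2023 and May 2027", so implantation ends in the same month as the last period.
- Section 4.5 starts the follow-up clock at the first treatment with the device and sorts visits into "30 days after surgery, 3 months after surgery, 6 months after surgery, and 1 year after surgery", each visit going to the nearest point.
- Sections 4.4.1 and 4.4.2 define the stroke, mortality and occlusion rates as proportions of all patients.
- Section 3 gives the objective as long-term safety and efficacy.

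No section says whether a patient belongs to a stage by implant date or by the date of each record, or whether the stage analyses accumulate.

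**The concern.** Follow-up is counted from each patient's surgery, but the stages are cut by calendar date. On the plain wording of Section 5.4, a patient treated late in one period has the procedure in one stage analysis and the later visits and events in the next.

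Section 5.4 leaves open how patients are assigned, and confining the data to the period causes trouble under either rule:

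- **By implant date, with data only from the same period.** Follow-up stops when the period closes. Section 4.4.3 notes that most occlusion after this type of device occurs within 12 months, so a 12-month period cuts off much of the main efficacy outcome for its own implants.
- **By record date.** A stroke in period 2 in a patient implanted in period 1 enters an analysis in which that patient's procedure does not appear, and the proportion has no defined denominator. Section 4.4.2 also stops image collection once Raymond-Roy Grade I is reached. Later-period images of earlier implants would then come only from patients who had not yet reached Grade I.

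At stake are the yearly rates of stroke, death and occlusion in a study meant to describe long-term results.

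**Working it through.** The Protocol gives no sample size, event count or stage-specific figure, so there is none to reproduce. The check is a count of calendar days.

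**Inputs**

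- Periods (Section 5.4), taken as whole months: 1 May 2023 to 31 May 2025 = 762 days; 1 June 2025 to 31 May 2026 = 365 days; 1 June 2026 to 31 May 2027 = 365 days. Total 1,492 days.
- Follow-up points (Section 4.5): 6 months taken as day 183, 1 year as day 365.
- Nearest-point boundary between 6 months and 1 year: (183 + 365)/2 = day 274.
- Assumption: implant dates are spread uniformly. The Protocol gives no accrual pattern.

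**Formula.** For a period of L days, the share of its own implants that reach day d inside it is (L − d)/L, or 0 if d ≥ L.

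| Point | Period 1 (L = 762) | Periods 2 and 3 (L = 365 each) |
|---|---|---|
| Day 183 | 579/762 = 76.0% | 182/365 = 49.9% |
| Day 274 (earliest visit filed as 1-year) | 488/762 = 64.0% | 91/365 = 24.9% |
| Day 365 | 397/762 = 52.1% | 0/365 = 0% |

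The zero does not depend on uniform accrual. An implant on 1 June reaches its anniversary on the next 1 June, one day after the period closes, so the longest possible follow-up inside period 2 or 3 is 364 days.

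**Split by record date instead.** Every day-365 visit in period 2 belongs to a patient implanted in period 1 (1 June 2024 to 31 May 2025). Every day-365 visit in period 3 belongs to a patient implanted in period 2. None belongs to a patient whose procedure is in the same period.

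**Over the whole window.** The implant and its day-365 point share a period for 397/1,492 = 26.6% of implant dates.

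**Cumulative cuts at the same dates.** The share of included implants that have reached day 365 is (days since 1 May 2023 − 365)/(days since 1 May 2023):

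- May 2025: (762 − 365)/762 = 397/762 = 52.1%
- May 2026: (1,127 − 365)/1,127 = 762/1,127 = 67.6%
- May 2027: (1,492 − 365)/1,492 = 1,127/1,492 = 75.5%

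At May 2027 the remaining 365/1,492 = 24.5% lack a full year under any way of dividing the data.

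**The case against.** **The stage reports need not be the only analysis.** Section 5.2 defines one dataset of all eligible patients with no calendar limit, Section 13 lists interim and final reports separately, and Section 14 describes a clinical study report. This stands. A reader might infer from 26.6% against 75.5% that the study as a whole loses most of its 1-year data. The documents do not support that; the contrast describes the stage analyses only.

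**Periods 2 and 3 are not empty of 1-year results.** This also stands. The nearest-point rule lets a visit from about day 274 count as 1-year, and by record date these periods also receive 1-year visits from earlier implants. The zero applies only to a full 365 days for a period's own implants.

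**The wording is not fully closed.** Section 5.4 does not exclude implant-date cohorts with later follow-up attached, and details may be in the SAP, which is not at hand. This stands in part. Division into periods, with analysis of the data from each, is what the Protocol itself fixes, and nothing in it makes the stages cumulative.

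**The schedule is attributed to the regulator.** The regulator's text is not available, so nothing can be said about whether it requires or forbids separate periods. The fix therefore leaves room for period tables.

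**Kaplan-Meier handles censoring.** Section 5.3.4 provides it for survival endpoints but does not name them, while stroke, mortality and occlusion are defined as proportions. It also cannot supply follow-up beyond the period's end.

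**Conclusion.** The point holds for the annual stage analyses. As written, Section 5.4 separates procedures from later outcomes. About 52% of period 1 implants and none of the period 2 or 3 implants can complete 365 days inside their own period; up to about 25% of implants in each of the later periods could have a visit labelled 1-year.

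A reader might infer that late events and late occlusion must be understated. The documents do not settle the direction. If later events are left out, rates fall; if earlier patients' events are set against only the new implants of a period, rates can rise.

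The percentages above zero assume uniform implantation, whole-month boundaries and the day counts used above. Rising or falling accrual would shift them. The zero at 365 days needs only the boundaries. The study is descriptive and a pooled final analysis remains possible, so this is a change that should be made rather than a flaw that invalidates the study.

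**What to change.** Keep the three reporting dates and any tabulation by period that the regulator asks for. Add to Section 5.4 and the synopsis:

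- Each stage analysis also covers all patients implanted since May 2023, with all data up to that cut-off.
- Patients are assigned to cohorts by date of first implant, and earlier cohorts are updated at every stage.
- At each follow-up point the denominator is the number of patients who have reached it, and that number is reported. Judge this by time elapsed from implant to cut-off, so that patients who have died stay in the denominator.
- At May 2027 about a quarter of implants will not have a full year of follow-up (24.5% under uniform accrual). Accumulating the data does not cure this, because implantation and the last period end together.

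The cost is small: revised wording, matching text in the SAP, and a cumulative data cut on which the same programs can be run.

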5.5 Management of Missing and Abnormal Values

Unless otherwise specified in a specific section, the missing values of baseline and safety data will not be filled.

For the missing efficacy endpoint, the missing values will be filled by the last carry-over method, the mean filling method or the multiple imputation method, and the specific filling rules and sensitivity analysis will be detailed in the statistical analysis plan.

5.6 Criteria for Eligible/Ineligible Clinical Study Results

This is a retrospective, multicenter, observational study, with both safety and efficacy assessments being descriptive analysis; therefore, no specific criteria for eligible criteria are set.

6 Data Management

6.1 Data Capture

Electronic Data Capture (EDC) will be used in this study, and clinical study data will be entered into eCRF by the investigators or authorized staff at the clinical research institutions. The investigators and authorized staff at the clinical research institutions will receive appropriate trainings before the initiation of clinical research institutions or data entering and appropriate measures will be adopted to protect the security of data.

The investigators will be responsible for maintaining all source documents and ensure they can be monitored by CRAs at each visit. In addition, the investigators shall submit a complete eCRF for every patient participating in the study, regardless of the duration of participation. The study number and patient number in all supporting documents (e.g., clinical research institution records) submitted with eCRF shall be checked carefully and all individual privacy (including the name of patient) shall be deleted, or measures shall be taken to make it difficult to identify patients to protect the privacy of patients.

6.2 Data Entering and Modification

The investigators or designers will be responsible for all entering, correction and modification of data. CRAs have no such permissions. All eCRF data will be submitted to the data manager. Any modification on data will be recorded by audit tracking, i.e., the reasons for modification, the name of the operator, time and date of the modification will be recorded. The role and permission of staff who are responsible for entering the data at the clinical research institution will be predetermined. CRAs or data management staff will raise queries in EDC for data and the staff at clinical research institution will be responsible for handling the queries. EDC system will record the audit tracking of queries, including the name of the investigator, time, and date.

6.3 Database Lock

The data manager, Principal Investigators (PIs), statistical analysis staff, sponsor and monitoring management staff will review the data together, complete the final definition and determination of population for analysis, and issue any necessary data queries. Then the database will be locked by data manager.

In general, locked database shall not be changed.

6.4 Database Transfer

The locked database will be transferred to statistical analysis staff for statistical analysis based on SAP.

7 Factors Influencing Study Success and Failure

7.1 Factors Influencing Study Success

The indications of the observational device is clear, and the composition and technical index are all in accordance with the related national and industry standards. This observational device, with clear principles and defined effects, complies with the applicable standards. At present, the devices used in this study have been approved and well used in China, and previous clinical studies have confirmed that they have good clinical effects and safety.

Before the start of the study, the clinical data records of each participating Institutions will be uniformly reviewed. The data records of the clinical research reference centers are standardized, the diagnosis and treatment records are complete, the data are traceable, and the original records are complete.

The study staff participating in the study have sufficient clinical experience and skilled operating ability. They also have sufficient patient resources, appropriate study teams, reasonable clinical study protocol, unified training for individuals participating in the study and unified recording procedure and standard of judgment. The investigators participating in the clinical study will be trained about the knowledge of the observational device and operating procedure by technicians of the observational device. The investigators shall follow the operating procedures strictly and all observations and laboratory results obtained during the clinical study shall be recorded and checked carefully to ensure authenticity and reliability of data and to ensure that all conclusions in the clinical study are based on source data.

7.2 Factors Influencing Study Failure

The non-compliance of study conducts with protocol, incomplete records of observations and laboratory test results during the clinical study, or lack of source data supporting may cause the failure of this study, but these factors are controllable.

Each patient participating in the clinical study will be clinically followed up comprehensively. The medical records of each patient will be fully monitored to observe the occurrence of complications closely and create detailed emergency treatment regimen. Regularly review the patient's medical records and record AE information in detail.

In conclusion, the probability of success for this clinical study is high, with a low likelihood of failure. However, the potential for failure is correlated with operational risks, patient-related factors, and the underlying disease characteristics.

8 Quality Control of Clinical Study

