4.3.4 Information of follow up

- Imaging Evaluation of a Target Aneurysm: DSA、MRA、CTA can be accepted.
- Treatment-related hospitalization information or adverse event information: Stroke, Death, Adverse Event, Serious Adverse Event.

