4.4 Endpoint

4.4.1 Safety Endpoint

(1) Stroke Rate

Definition: The stroke rate refers to the proportion of stroke patients in the total number of patients.

Collection Content: Record the date of stroke, type (ischemic or hemorrhagic), severity (mild, moderate, severe), location and cause, treatments, or other interventions for stroke, and whether the

stroke resulted in the patient's death. Also assess the relationship of the stroke event to the observational device and the patient's concurrent antithrombotic therapy. All stroke events are assessed by the CEC.

(2) All-cause Mortality

Definition: Mortality refers to the proportion of dead patients in the total number of patients.

Collection Content: Record the date of the death event and whether it was neurogenic. Evaluate the relationship of the death event to the observational device. Neurogenic death is defined as a death event directly resulted from a neurologic cause judged by the Clinical Event Committee (CEC).

(3) Lesion-Related Symptoms or Signs Rate

Definition: Lesion-related symptoms or signs rate refers to the proportion of patients with lesion-related symptoms or signs to total patients.

Collection Content: All neurological related symptoms which were not present at baseline or worsened from baseline will be record including headache, hemiplegic paralysis, seizure, aphasia, stroke, bleeding (including intracerebral, subarachnoid hemorrhage, retroperitoneal, others), facial nerve pain, seizures, vision loss, aphasia, hemiplegia, oculomotor nerve palsy, neck pain or stiffness, loss of consciousness, meningeal irritation, pre-retinal hemorrhage, increased intracranial pressure, other aneurysm-related symptoms, or abnormal signs (list specific symptoms or abnormal signs).

(4) Lesion-Related Complication Rate

Definition: Lesion-related complication refers to the proportion of patients with lesion-related complication to total patients.

Collection Content: Record whether the following complications occurred during the procedure. Principal Investigator (PI) shall evaluate the relationship between complications and observational device, other interventional devices, and surgical procedures.

- Complications of arterial puncture: including puncture site pain, puncture site local bleeding, injury to the puncture artery or adjacent nerves,;
- Dissection or perforation of the parent artery,
- Rupture or perforation of the aneurysm,
- Vasospasm;
- Stent thrombosis,
- Other complication

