10.2.2 Reporting of SAEs

For SAEs, investigators shall conduct a comprehensive analysis and assessment of the SAE immediately after becoming aware of it, including its severity and relationship to the observational device. For suspected SAE related with medical device, investigators shall report to relevant personnel. For SAEs lead to death or SAEs lead to serious injury, reports must be submitted within reported within the prescribed time frame.

11 Clinical Event Committee

The Independent Clinical Event Committee (CEC) will evaluate safety endpoints data and the sponsor will appoint a CEC composed of physicians (not investigators) to rule uniformly adjudicate all SAE and/or AEs associated with the observational device or observational procedure identified. Only CEC's determinations of the collected data (Data collection includes patient medical records, laboratory tests, and, if necessary, patients' imaging data) were used for the analysis of safety endpoints.

12 Protocol Amendments

If there is any modification to the protocol after EC approval, a "protocol revision statement" or revised protocol is required, which shall be signed and confirmed by the sponsor and the coordinating investigator and approved by the EC before implementation.

13 Direct Access to Source Data and Documentation

Source data refers to the original records of clinical findings, observations, and other activities in a medical device clinical study, as well as all information in certified copies, which can be used for the reconstruction and evaluation of the clinical study.

Source documents refer to printed documents, visual files, or electronic files that contain source data.

The archived materials for this clinical study include: (1) clinical study protocol; (2) electronic case report forms (eCRFs); (3) informed consent forms (If any); (4) original medical records of the patients; (5) statistical analysis reports; (6) all other materials such as interim reports and final summary reports of the clinical study.

Investigators must carefully complete all study documents, including the confirmation of all participated patients (effectively verifying different records, such as eCRFs and original hospital records), all original signed informed consent forms of patients (if any), and detailed records in all eCRFs. After the study is completed, all clinical study documents shall be submitted to the clinical research institution for safekeeping.

14 Clinical Study Report

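### Stroke and mortality rates divide by all patients whatever their follow-up, so patients with no later record are in effect scored event-free and any unseen event lowers the rate

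*Protocol*

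**What the plan says.** Protocol 4.4.1 defines both endpoints as plain proportions: "The stroke rate refers to the proportion of stroke patients in the total number of patients", and "Mortality refers to the proportion of dead patients in the total number of patients". Neither definition has a time point. Section 5.2 supplies the denominator: "The dataset will consist of all study patients who meet the inclusion and exclusion criteria". Section 4.2.1 asks only that the patient was treated with the device and that clinical data are available, so no record after the procedure is needed to be counted. Section 5.5 adds that "the missing values of baseline and safety data will not be filled".

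On how events reach the database, 4.3.4 lists "Treatment-related hospitalization information or adverse event information: Stroke, Death, Adverse Event, Serious Adverse Event". Section 11 bases the safety endpoints solely on what the event committee decides: "determinations of the collected data (Data collection includes patient medical records, laboratory tests, and, if necessary, patients' imaging data) were used for the analysis". Section 7.2 tells sites to "Regularly review the patient's medical records and record AE information in detail". Section 9.2 says that a waiver of consent will be requested because the study is retrospective.

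Section 5.3.4 gives binary endpoints an exact binomial interval and survival endpoints a Kaplan-Meier estimate with censoring. It does not say which endpoints belong to which group.

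**The concern.** The study's objective is long-term safety. Section 4.1.1 cites a regulatory requirement for long follow-up of every implanted patient, and 4.4.3 cites clinical follow-up of deaths and strokes within 6 months. A proportion over all patients supports such a claim only if each patient's status at the stated time is known.

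Here a patient can qualify on procedure data alone and leave no later trace. A death at home, or a stroke treated at another hospital, may not appear in the participating site's records. The patient still adds one to the denominator. The same holds for a patient implanted shortly before the data cut. The exact binomial interval gives no warning, because patients of unknown status make it narrower. A low reported rate could then reflect few events, or few patients whose outcome was seen, and a reader could not tell which.

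**Working it through.** The protocol states no sample size, event rate or loss to follow-up, so there is no figure of its own to reproduce. All numerical inputs below are assumptions.

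**1. Direction under the 4.4.1 definition.** Let p be the true risk, f the share of patients with no later record, and RR their risk relative to patients with records. Assume that none of their events is seen.

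- Risk in patients with records: q = p / ((1 − f) + f × RR)
- Rate reported over all patients: (1 − f) × q
- Rate over patients of known status: q. Kaplan-Meier also gives q if the others are censored at the procedure.

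Example with p = 4%, f = 20%, RR = 3: q = 0.04 / (0.8 + 0.6) = 2.86%, and the reported rate is 0.8 × 2.86% = 2.29%.

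Results for p = 4%, shown as reported over all patients / known status or censored:

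| f | RR = 0.5 | RR = 1 | RR = 3 |
|---|---|---|---|
| 10% | 3.79% / 4.21% | 3.6% / 4.0% | 3.0% / 3.33% |
| 20% | 3.56% / 4.44% | 3.2% / 4.0% | 2.29% / 2.86% |
| 30% | 3.29% / 4.71% | 2.8% / 4.0% | 1.75% / 2.5% |
| 40% | 3.0% / 5.0% | 2.4% / 4.0% | 1.33% / 2.22% |

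The all-patient proportion is below 4% in every cell. The censored or known-status figure is correct at RR = 1, too low at RR = 3 and too high at RR = 0.5. The sign of the bias is therefore fixed only under the total-patient definition.

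**2. Effect on the interval.** Assume 500 patients, 20 true deaths (4.0%), 20% without a later record and RR = 1, so that 16 deaths are seen. Over all patients: 16/500 = 3.2%, exact 95% CI 1.8 to 5.1. Over patients of known status: 16/400 = 4.0%, CI 2.3 to 6.4. The all-patient rate is both lower and apparently more precise.

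**3. Time point not yet reached.** If implants were spread evenly over the 48 months from May 2023 to May 2027 and data were cut at the end, 12/48 = 25% of patients could not have a full year of follow-up, yet all would stay in the denominator.

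**4. Worst-case bounds.** Assume 300 patients and 6 recorded deaths: 6/300 = 2.0%, exact 95% CI 0.7 to 4.3. If 10%, 15% or 20% have unknown status and every one of them had died, the rates would be (6 + 30)/300 = 12%, (6 + 45)/300 = 17% and (6 + 60)/300 = 22%. These limits show what the data could not exclude. They do not estimate the bias.

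**The case against.** The strongest reply is that the protocol nowhere says that a patient without later records is alive or stroke-free. Section 8.2 has unknown or unavailable information recorded as such. Section 5.5 leaves missing safety values missing, and scoring them as no event would itself be a way of filling them. Section 5.3.4 provides Kaplan-Meier with censoring, and the dates of death and stroke are collected. This stands as far as it goes: a reader might infer an explicit rule that unknown means alive, and there is none. But 4.4.1 still fixes both rates over the total number of patients, and recording a status as unknown does not remove the patient from that total. Section 5.3.4 would answer the point only if it named death and stroke as survival endpoints, which it does not.

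A reader might also infer that charts are the only source of events. Section 7.2 promises comprehensive clinical follow-up of each patient, and the list of sources in Section 11 is not stated to be exhaustive. The fair statement is that no contact procedure or vital-status check is described. The record-review sentence in 7.2 concerns the recording of adverse events; it sets neither how deaths are found nor the denominator.

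Two further inferences fail. One is that the unseen death is itself what ends the chart, so that censoring cannot help. The documents do not support this: a chart may also end because the patient is well, and 4.4.2 stops imaging collection once Raymond-Roy Grade I is reached. The other is that 4.3.4 captures only treatment-related deaths. The qualifier is most naturally read as attached to hospitalization; adverse events count whether or not related to the device (10.1.1), and the mortality endpoint is all-cause.

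Finally, analysis detail may be left to the SAP, which was not available here. That covers the choice of displays, but not a denominator that the protocol itself fixes.

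**Conclusion.** The concern holds in a limited form. Sections 4.4.1, 5.2 and 5.5 together have the arithmetic effect of scoring patients with no later record, or not yet at the time point, as event-free. Stroke rate and all-cause mortality are then biased downward if any events in those patients go unseen. Whether this happens, and how far, depends on the share without later records and on their risk, and the protocol gives neither. For an assumed true risk of 4% and none of these patients' events seen, the reported rate runs from 3.79% (10% without a record, half the risk) to 1.33% (40% without a record, three times the risk).

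It would go too far to say that the reported rates are too low as an established fact, or to read 12% to 22% as the likely true mortality. Those figures require every patient of unknown status to have died, under assumed inputs.

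**What to change.** In 4.4.1 and 5.3.4, choose one of two definitions and state it.

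- **Time-to-event:** name death and stroke as survival endpoints, censored at the last dated record, with numbers at risk at each time point.
- **Fixed-time rates:** report at 30 days, 6 months and 1 year, which are among the follow-up points already in 4.5. Class each patient as event; event-free with a dated record at or after that point; time point not yet reached; or status unknown. Judge the third class from implant date and data cut alone, for patients with and without events alike, so that early events are not counted against a denominator missing their event-free contemporaries.

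The nearest-date rule in 4.5 does not replace the second class: a record at 10 months is nearer to 1 year than to 6 months, but does not show status at 1 year.

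Print the number of unknown status beside each stroke and mortality rate. Give bounds that count the unknowns as all non-events and as all events, labelled as a sensitivity display. Censoring alone is not enough, since the table above shows that it can err in either direction. Rewording the hospitalization item in 4.3.4 would be at most a clarification.

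The cost is a little programming and one table. Follow-up is already assigned by date, though an eCRF item for the date of last known status may be needed, because the listed items do not include one. The changes recover no missed event, and the safety rates will look less favourable and less certain.
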